APPENDIX III – DETAILED MBT PROCEDURE

Preparation of the study subject

Once enrolled, the patients will perform the breath test if they meet the criteria of the patient population. In preparation for each breath test the patient will be asked to comply with the following instructions:

1. Fast 8 hours prior to the breath test.
2. Refrain from use of caffeine, propranolol, within the last 24 hours. Refrain from use of acetaminophen-related medications (e.g. Tylenol) 24 hours prior to the breath test.
3. Refrain from use of alcohol 24 hours prior to the breath test.

Preparation of ¹³C-Methacetin

Exalenz Bioscience Ltd. will provide 75 mg ¹³C-Methacetin doses in a 0.05% solution of ¹³C-Methacetin in purified water, supplied, in amber thermoplastic polyester (PET) bottles with a child resistant plastic stopper (75mg of ¹³C-Methacetin in 150mL purified water). No preparation is needed other than pouring the contents of the solution into a cup for ingestion if administered orally.

Performance of the breath test

Only trained personnel (doctors, nurses) will perform the breath test procedure. The actual breath collection is automatically done by the device and is not operator dependent. If the patient was not connected properly with the cannula (e.g. the breath does not reach the device), the *BreathID[®] MCS* device will prompt the operator to adjust the cannula.

1. Turn on device from switch in rear and allow up to 1 hour for warm-up to complete. To perform the test, ensure that the *BreathID[®] MCS* console screen shows that the device is in the 'Ready' state.
2. The cannula will be attached to the *BreathID[®] MCS* device and to the patient. The *BreathID[®] MCS* device will be activated and will collect the patient's baseline *exhale^d* breath for approximately 15-20 minutes.
3. The solution ¹³C-Methacetin is poured into a disposable cup and administered to the patient. The solution should be administered by a medical practitioner registered on the delegation log or a research nurse if specific training for administration has been given. Immediately after ingestion, the operator will press the "continue" button and activate the

Exalenz Bioscience Ltd.	Last update on: Nov 21, 2016
Study Title: Clinical Study of the BreathID[®] MCS System to train the algorithm for the ¹³C-Methacetin Breath Test (MBT) in assessment of Portal Hypertension in Patients with Compensated Liver Cirrhosis	Protocol No.: CSPH-EX-0414 Version: 1.5
Document N^o: CSD00076	Page 72 of 72

actual measurement. CO₂ production with ¹³C may be visible within a few minutes in cases with relatively functional livers.

Note: In rare cases the administration of fluids may cause vomiting. If this happens the test should be aborted and repeated the next day. The expected adverse event should be reported in the appropriate CRF section.

4. The patient should remain in a seated position breathing in a normal manner for up to 75 minutes, whilst data are collected.
5. The *BreathID[®] MCS* device continuously measures and analyzes the patient's exhaled breath in real time. As the ¹³C-Methacetin is metabolized, the value of the ¹³CO₂/¹²CO₂ ratio in the exhaled breath will change and will be calculated in real time by the *BreathID[®] MCS* device. The device will prompt the operator to enter patient details such as weight and height, age and gender. The *BreathID[®] MCS* device will calculate the *MBT* variables.
6. If at any time the device does not detect patient's breath, or if there is any other deviation from the desired test requirements, the device will produce an appropriate warning signal.
7. At the completion of the procedure, the cannula is removed and the patient is disconnected from the *BreathID[®] MCS* device.

The patient will be under the supervision of the physician or any other qualified medical staff during the entire test.

The operators will be trained how to terminate the breath test early. In the following situations, the *MBT* test will be terminated and a test termination form will be completed:

1. The patient vomits.
2. The patient is inadvertently disconnected.
3. The *BreathID[®] MCS* device malfunctions (In this case, the operator will complete a technical complaint form in addition to the test termination form and contact Exalenz immediately for further instructions)

In all these cases, the next *MBT* cannot be repeated the same day. An entry will be made in the drug/kit accountability log and the bottles will be kept for inspection by the study monitor.

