Note2: If patient is using a stable dose of beta blockers both the MBT and the HVPG procedures should be performed while continuing the stable dose even on the morning of each test.

Note3: If patient has HCC, breath test has to be performed on the day of HVPG measurement.

^c The measurement will be performed in a uniform way including following a standardized procedure to measure HVPG pressures (see Appendix II), either before or after the MBT, with certain limitations detailed in the protocol.

Exalenz Bioscience Ltd.	Last update on: Nov 21, 2016
Study Title: Clinical Study of the BreathID[®] MCS System to train the algorithm for the ¹³C-Methacetin Breath Test (MBT) in assessment of Portal Hypertension in Patients with Compensated Liver Cirrhosis	Protocol No.: CSPH-EX-0414 Version: 1.5
Document N^o: CSD00076	Page 15 of 72

Rules of discontinuations (Subject and/or Study):

1. Withdrawal of patients from the study if they have a CTCAE (Common Terminology Criteria for Adverse Events) Grade 3 or higher regardless of whether the event is attributed to the drug unless it is caused by an accident that could not reasonably be attributable to the drug (CTCAE: Common Terminology Criteria for Adverse Events Version 4.0).
2. Discontinuance of study, if ≥ 2 patients on Methacetin develop the same CTCAE Grade 3 event or 1 patient develops a CTCAE Grade 4 or higher event due to the breath test.

Data Analysis / Statistics:

A ROC analysis will be used to determine the optimal parameter and cut-offs for required performance measures sensitivity and specificity.

All efficacy analysis will include the point estimates of sensitivity, specificity, PPV and NPV with respective exact 95% confidence intervals. The respective Positive and Negative Predictive Values (PPV and NPV) will be presented as a function of possible CSPH prevalence and will include the prevalence of the enrolled population.

Exalenz Bioscience Ltd.	Last update on: Nov 21, 2016
Study Title: Clinical Study of the BreathID[®] MCS System to train the algorithm for the ¹³C-Methacetin Breath Test (MBT) in assessment of Portal Hypertension in Patients with Compensated Liver Cirrhosis	Protocol No.: CSPH-EX-0414 Version: 1.5
Document N^o: CSD00076	Page 16 of 72

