11.1 Inclusion Criteria

1. Adult men or women (≥ 18 years of age)
2. Patient (or legal guardian) can sign an Informed Consent Form.
3. Known chronic liver disease with cirrhosis confirmed by either:
 - a. liver biopsy or
 - b. clinical (palpable left lobe, splenomegaly) and laboratory (platelets $< 150,000/\text{mm}^3$ or albumin $< 3.8\text{g/dL}$, or INR > 1.3) evidence of cirrhosis and/or
 - c. imaging studies by abdominal sonography, computer assisted axial tomography, or magnetic resonance imaging, showing a nodular liver and/or enlarged spleen and/or portosystemic collaterals with portal vein patency and/or minimal ascites, and/or colloid shift on a colloid-isotope liver-spleen scan or measurements of liver stiffness suggestive of cirrhosis
4. Europe: Indicated to undergo HVPG testing
US: Consented for HVPG
5. Can tolerate an overnight (8-hour) fast
6. For patients treated with statins: They have to be on a stable dose for at least 4 weeks prior to any study related tasks (MBT or HVPG measurement)
7. For patients treated with beta blockers: They have to be on a stable dose for at least 6 weeks prior to any study related tasks (MBT or HVPG measurement)
8. For patients who stopped their treatment with beta blockers: Their last dose should be at least 6 weeks prior to any study related tasks (MBT or HVPG measurement)

Note: In case patient has HCC, breath test has to be performed on the day of HVPG measurement.

11.2 Exclusion Criteria:

1. Decompensated cirrhosis as clinically defined by the occurrence of any of the following: ascites, hepatic encephalopathy, variceal bleeding (active upper GI bleeding) or hepatorenal syndrome
2. Renal failure (creatinine $> 2.5\text{ mg/dl}$)
3. Known acute renal tubular disease
4. Known hypotension (Systolic Pressure $< 100\text{mmHg}$)
5. Hypocoagulability defined as PT > 6 and INR > 2.3
6. Congestive heart failure (assessed clinically as NIHA > 2)

Exalenz Bioscience Ltd.	Last update on: Nov 21, 2016
Study Title: Clinical Study of the BreathID[®] MCS System to train the algorithm for the ¹³C-Methacetin Breath Test (MBT) in assessment of Portal Hypertension in Patients with Compensated Liver Cirrhosis	Protocol No.: CSPH-EX-0414 Version: 1.5
Document N^o: CSD00076	Page 36 of 72

7. Known pulmonary hypertension (right ventricular systolic pressure > 45 mm Hg,)
8. Uncontrolled diabetes mellitus (HBA1C >9.5gr%)

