9. Concurrent prednisone or immunosuppressive treatment, if therapy and/or response to treatment are not stable for at least 3 months
10. Documented hepatocellular carcinoma lesion larger than 3cm and/or multifocal lesions and/or evidence of vascular invasions
11. Gastric bypass surgery or extensive small bowel resection
12. Total parenteral nutrition
13. Any organ transplant recipient
14. Pregnant or breast feeding
15. Allergy to acetaminophen and/or other related medications.
16. Documented drug-related concurrent hepatotoxicity or drug-related silent steatosis or drug-related fibrosis (e.g. amiodarone, methotrexate and tamoxifen).
17. Uncontrolled malabsorption or diarrhea
18. Documented non-cirrhotic PHT, partial / complete portal venous occlusion, hepatic venous occlusion, previous PHT surgery, or placement of a transjugular intrahepatic portosystemic shunt (TIPS)
19. Primary or secondary biliary cirrhosis, primary or secondary sclerosing cholangitis, hepatic sarcoidosis, or other cholestatic disorders
20. Subjects unable to perform the MBT within 7 days of HVPG procedure
21. Subject should not have taken any of the following for at least 48 hours prior to the breath test: Acyclovir , allopurinol, carbamazepine, cimetidine, ciprofloxacin, daidzein, (herbal) disulfiram, echinacea, enoxacin, famotidine, fluvoxamine, methoxsalen, mexiletine, montelukast, norfloxacin, phenylpropanolamine, phenytoin, propafenone, rifampin, terbinafine, ticlopidine, thiabendazole, verapamil, zileuton or any medication that might interfere with Methacetin metabolism or might affect CYP 1A2
22. Subject should not have taken amiodarone within the last 30 days prior to the breath test or HVPG procedure
23. Splenomegaly secondary to inflammation/infection or hematologic malignancy.
24. Last dose of HCV treatment received within the last 3 years.

11.3 On the day of the MBT:

1. 8 hours fasting prior to MBT including all PO morning medications except for beta blockers
2. No Smoking on the day of the MBT

Exalenz Bioscience Ltd.	Last update on: Nov 21, 2016
Study Title: Clinical Study of the BreathID[®] MCS System to train the algorithm for the ¹³C-Methacetin Breath Test (MBT) in assessment of Portal Hypertension in Patients with Compensated Liver Cirrhosis	Protocol No.: CSPH-EX-0414 Version: 1.5
Document N^o: CSD00076	Page 37 of 72

3. No caffeine within 24 hours prior to MBT
4. No paracetamol (acetaminophen) based medications within 24 hours prior to MBT

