5. No general anesthesia or sedation within 24 hours prior to MBT
6. No alcohol within 24 hours prior to MBT
7. Patient should be symptom free of any prior intervention (e.g. biopsy)

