13 STUDY PROCEDURES

13.1 General

1. The study will be conducted in compliance with this protocol, with GCP standards, and the applicable regulatory requirements.
2. This study will be cross-sectional, where patients will be enrolled, if possible, in a consecutive manner so as to prevent any bias. All patients with cirrhosis and without clinical signs of complications should be screened and reason for non-suitability documented.
3. Patients' relative or other representative will sign a consent/assent form prior to study participation.
4. A CRF will be filled out for each patient and all data will be collated incorporating all demographics, detailed clinical history, physiological variables, radiological data, biochemical data and organ support provided (cardiovascular, respiratory, renal, hepatic, neurological) and all baseline characteristics.
5. HVPG procedure will be performed in a standardized fashion in all study centers (see section 13.4 and Appendix II).
6. In addition, the tracings will be read at a centralized location by an independent expert reader. This independent analysis will be done by an expert reader blinded to the breath test results.
7. The *MBT* will be performed within 7 days (prior or post) of the HVPG procedure using a single dose of 75mg ¹³C-Methacetin. Note that the same

Exalenz Bioscience Ltd.	Last update on: Nov 21, 2016
Study Title: Clinical Study of the BreathID[®] MCS System to train the algorithm for the ¹³C-Methacetin Breath Test (MBT) in assessment of Portal Hypertension in Patients with Compensated Liver Cirrhosis	Protocol No.: CSPH-EX-0414 Version: 1.5
Document N^o: CSD00076	Page 42 of 72

policy should be applied with regards to the use of beta blockers as for the HVPG procedure for those patients that are treated with beta blockers. In case patient has a HCC, breath test has to be performed on the day of HVPG measurement.

8. If patient is using a stable dose of beta blockers, both the MBT and the HVPG procedures should be performed while continuing the stable dose even on the morning of each test.
9. All investigators will be blinded to the *MBT* score results until the end of the study recruitment. The *MBT* results will therefore not affect the current patient management.
10. Safety follow up will be done during the entire period of the study, and any adverse events will be recorded according to GCP ICH guidelines. Section 16.6 relates to the reportable and non-reportable SAEs.

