13.4 Principles of the Hepatic Venous Pressure Gradient (HVPG)

In order to standardize the measurements of the HVPG in the study the main procedure steps, derived from the common standards of care practice⁽¹⁰⁾, are described below in Appendix II.

Under conscious sedation and with non-invasive vital sign monitoring (ECG, arterial blood pressure and pulse oximetry) the right jugular vein (or the femoral or antecubital vein) is catheterized, a venous introducer is placed and a balloon-tipped catheter is advanced under fluoroscopic control into the inferior vena cava and a hepatic vein, to measure pressures. This is a moderately invasive technique that is only being performed as part of the clinical evaluation of the patient (and not solely for the purpose of the clinical trial) in common with other routine procedures that are carried out in patients with chronic liver injury.

Exalenz Bioscience Ltd.	Last update on: Nov 21, 2016
Study Title: Clinical Study of the BreathID[®] MCS System to train the algorithm for the ¹³C-Methacetin Breath Test (MBT) in assessment of Portal Hypertension in Patients with Compensated Liver Cirrhosis	Protocol No.: CSPH-EX-0414 Version: 1.5
Document N^o: CSD00076	Page 44 of 72

Free hepatic venous pressure is measured by maintaining the tip of the catheter “free” in hepatic vein, 2-4 cm from its opening into the vena cava. Wedge hepatic venous pressure is measured by occluding the hepatic vein by inflating a balloon at the tip of the catheter. The wedged hepatic venous pressure is measured until the value remains stable over 30-40 seconds. All measurements are performed in triplicate, permanent tracings are captured on a computer or chart recorder. The difference between the free and wedged hepatic venous pressures is the HVPG. Adequate occlusion of the hepatic vein is confirmed after pressure measurement, by slowly injecting 5cc of contrast into the vein that should show a typical “wedged” pattern without reflux of the contrast or its washout through communications with other hepatic veins.

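### Appendix III withholds propranolol for 24 hours before the breath test, while section 13.1 and the synopsis require a stable beta-blocker dose to continue on the morning of each test

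*Combined protocol and SAP*

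**What the plan says.** Section 13.3 contains no procedure of its own; it refers sites to Appendix III and the Investigator Brochure. Under preparation of the study subject, Appendix III item 2 says "Refrain from use of caffeine, propranolol, within the last 24 hours". It applies before each breath test and makes no exception for patients on a stable dose.

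Elsewhere the protocol says the opposite:

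- Section 13.1 item 8, for patients on a stable beta-blocker dose: "both the MBT and the HVPG procedures should be performed while continuing the stable dose even on the morning of each test".
- Synopsis Note2 gives the same rule: "beta blockers both the MBT and the HVPG procedures should be performed while continuing the stable dose even on the morning of each test".
- Section 13.1 item 7, on the MBT, says that the same "policy should be applied with regards to the use of beta blockers as for the HVPG procedure".
- Section 11.3 item 1 exempts these drugs from the morning-medication hold: "8 hours fasting prior to MBT including all PO morning medications except for beta blockers". This does not itself require the dose, but it permits it.

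The synopsis version of that fasting line lacks the exemption.

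**The concern.** An operative instruction to sites contradicts the protocol's own rule on a drug class whose effect the study sets out to examine. Secondary endpoint 4 (section 12.3) asks whether beta blockers affect the correlation of MBT with HVPG. Under sections 12.5 and 12.7.6, a significantly different correlation in beta-blocker users is one of several findings that may lead to enlarging the study from 200 to as many as 400 patients.

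That comparison is interpretable only if being on a beta blocker means the same thing at both tests and at every site. If some sites hold propranolol before the MBT and others do not, the group labelled as users contains different drug states. It also becomes unclear which patients belong in the protocol-deviation listing of section 12.7.3, since following either text departs from the other.

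**Working it through.** No arithmetic applies. The check is whether the texts can be reconciled and, if not, what follows.

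**Who is caught.** Inclusion criterion 7 admits patients treated with beta blockers only on a dose stable for at least 6 weeks. Every eligible propranolol user is therefore a stable-dose user, covered by 13.1 item 8 and by Appendix III item 2. Users of other beta blockers are not affected, because Appendix III names only propranolol.

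**Can the texts be reconciled?**

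1. Appendix III might be meant only for patients not on a stable dose. It does not say so, and criterion 7 excludes treated patients of that kind.
2. Exclusion 21 bars listed drugs, and any others that might affect methacetin metabolism or CYP 1A2, for 48 hours. Propranolol is not listed. If the general clause did cover it, the hold would be 48 hours rather than 24, and 13.1 item 8 would still say to continue.
3. HVPG might carry a matching hold. Appendix II contains none, so following Appendix III also breaches the same-policy rule in 13.1 item 7.
4. Section 11.3 might repeat the hold. Its 24-hour restrictions cover caffeine, paracetamol, anaesthesia or sedation, and alcohol, but not propranolol.

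None of these readings removes the conflict.

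**What a site following Appendix III could produce.** The two tests may be up to 7 days apart. When they fall on one day, their order is constrained: section 11.3 item 5 says "No general anesthesia or sedation within 24 hours prior to MBT", and section 13.4 describes HVPG as done "Under conscious sedation and with non-invasive vital sign monitoring". A same-day MBT should therefore come first. Same-day testing is compulsory for some patients: "In case patient has HCC, breath test has to be performed on the day of HVPG measurement".

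| Text followed for the MBT | Timing | Propranolol at MBT | Propranolol at HVPG | Other beta blockers, both tests |
|---|---|---|---|---|
| 13.1 item 8 | Any | On | On | On |
| Appendix III | Different days, dose continued for HVPG | Withheld | On | On |
| Appendix III | Same day, dose taken between tests | Withheld | On | On |
| Appendix III | Same day, dose taken after HVPG | Withheld | Withheld | On |

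The second and third rows mismatch the two tests within a patient. In the last row the tests match, but the patient differs from other beta-blocker users and from propranolol users at sites following 13.1.

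**The case against.** The strongest reply is that the protocol's intention is clear and the conflict is one stray word. Section 13.1 items 7 and 8, Note2 and the 11.3 exemption all point to continuing the dose, and item 7 comes close to a tie-breaker because it ties MBT handling to HVPG handling. This is right about intent, and it is the main reason for correcting Appendix III rather than the body. It does not remove the conflict: no text states which section prevails, and staff preparing a patient are sent to Appendix III.

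A second reply is that the hold may be deliberate, since Appendix III places propranolol beside caffeine and acetaminophen, and the Investigator Brochure, also cited in 13.3, is not available here. That cannot be excluded, so the sponsor should confirm intent. A deliberate hold would still leave 13.1 and Note2 in contradiction with it.

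A third reply is that no analytic harm has been shown. Section 5.6 reports no apparent influence of non-selective beta blockers on the correlation in a 21-patient subset, the analyses are descriptive, and the increase to 400 is optional. All of this stands as a limit on importance. The subset did not, however, test a 24-hour hold, and it cannot settle a question the study itself poses as a secondary endpoint.

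**Conclusion.** The contradiction is real and stands in the current text. A patient on stable propranolol cannot comply with both Appendix III item 2 and section 13.1 item 8.

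Its size cannot be quantified. The documents give no number or share of propranolol users and no effect of a 24-hour hold on MBT or HVPG. Exposure is limited to propranolol users at sites that follow Appendix III. The consequence is possible mixing of drug states in secondary endpoint 4, and through it in one of the triggers for enlarging the sample. No effect on the primary objective is claimed; the algorithm is to be validated in a separate study (section 12.1).

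The conclusion rests on propranolol being a beta blocker and on reading Appendix III as an instruction to sites, which section 13.3 makes it. It should be corrected, but it is not critical.

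**What to change.** - Confirm with the sponsor, against the Investigator Brochure, that continuing the stable dose is the intended rule. Then delete propranolol from Appendix III item 2, so that 13.1 item 8 and Note2 govern.
- As a tidy-up, add the four-word beta-blocker exception to the synopsis fasting line so that it matches 11.3 item 1.
- Only if patients have already been tested under the hold, identify them and repeat the secondary endpoint 4 comparison without them as a sensitivity analysis. Section 13.1 item 13 has concurrent medication recorded, but nothing says that a skipped dose or last-dose time is captured, so sites may have to be asked.

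The text change is one word deleted and four added, with no new CRF field. The practical cost is a short amendment, submitted to the relevant ethics committees under section 14.1; the synopsis lists eight institutions.
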